7.7.4 Secondary Objective #3

Rate of Secondary Procedures

Analysis Dataset:

Treated Analysis Set per section **Error! Reference source not found..**

Analysis Method:

Secondary procedure rate will be summarized cumulatively through 12 months as the number of procedures per person-years as well as the number and percentage of subjects having one or more procedures in the Treated population. This summary will be presented overall and by type of procedure (surgical or percutaneous). Additionally, the number of secondary procedures will be summarized categorically as the number and percentage of subjects with 0, 1, 2, 3, or 4 or more procedures.

Summaries specific to PTA/balloon maturation interventions will be provided. These summaries will be based on secondary procedures that include a PTA/balloon maturation intervention, whether performed alone or in combination with other interventions. The summaries will be presented for interventions performed post-AVF creation through 12 months. The summaries will include the number of PTA interventions performed, whether the PTA was performed in combination with other interventions, the rate of intervention in person-years, the location and average balloon size. Similar summaries will be provided for stent, embolization, and valvulotomy interventions, presented cumulatively through 12 months.

This endpoint will also be summarized by type of procedure (e.g. banding, balloon maturation, transposition/elevation/ superficialization, etc.), indication (due to stenosis, due to AE, etc.), procedure success and association with any AEs.

Endpoint Definition:

Secondary procedures are surgical or percutaneous interventions designed to mature or maintain the AVF or re-establish flow. Secondary procedures are procedures subsequent to completion of the AVF creation procedure.

Additional Analysis:

- The association between the occurrence of acute anastomotic disruption or pseudoaneurysm and the secondary procedure rate for the Treated population. The mean number of secondary procedures will be summarized cumulatively and stratified by subjects who experienced anastomotic disruption or pseudoaneurysm and those who did not.
- The association between the occurrence of early occlusions and the secondary procedure rate for the Treated population. The mean number of secondary procedures will be summarized for subjects who experienced an early occlusion and those who did not.

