**Analysis Method:**

Secondary procedure rate will be summarized cumulatively through 12 months as the number of procedures per person-years as well as the number and percentage of subjects having one or more procedures in the Treated population. This summary will be presented overall and by type of procedure (surgical or percutaneous). Additionally, the number of secondary procedures will be summarized categorically as the number and percentage of subjects with 0, 1, 2, 3, or 4 or more procedures.

Summaries specific to PTA/balloon maturation interventions will be provided. These summaries will be based on secondary procedures that include a PTA/balloon maturation intervention, whether performed alone or in combination with other interventions. The summaries will be presented for interventions performed post-AVF creation through 12 months. The summaries will include the number of PTA interventions performed, whether the PTA was performed in combination with other interventions, the rate of intervention in person-years, the location and average balloon size. Similar summaries will be provided for stent, embolization, and valvulotomy interventions, presented cumulatively through 12 months.

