4.2.1 Secondary Endpoints

The following secondary endpoints to be evaluated in this study are as follows:

1. Primary patency through 12 months post-AVF creation:

Defined as freedom from access thrombosis or any intervention designed to facilitate, maintain or reestablish patency measured from time of access creation through 12 months.

2. Assisted primary patency through 12 months post-AVF creation:
Defined as freedom from access thrombosis from time of access creation through 12 months.
3. Secondary procedure Rate:
Defined as the percentage of subjects having one or more surgical or percutaneous interventions designed to mature or maintain the AVF or re-establish flow. Secondary procedures are procedures subsequent to completion of the AVF creation procedure. This endpoint will also be summarized by type of procedure, indication, procedure success and association with any adverse events (AEs).
4. Overall patient safety:
A full characterization of all adverse events during the study.

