4.3.1 Ancillary Endpoints

The following ancillary endpoints to be evaluated in this study are as follows:

1. Functional Patency Rate Through 12 months: *Defined as freedom from access abandonment from the time of first two-needle cannulation.*
2. Physiological Maturation Rate at 3, 6, and 12 months: *Defined as the percentage of access sites with access vessel minimum blood flow rate $\geq 500\text{mL/min}$ and minimum diameter $\geq 5\text{mm}$ as measured by duplex ultrasound.*
3. Functional Cannulation Success Through 12 months: *Defined as the time to achieve successful use of the endovascular AVF, with two-needle access and at least two hours of dialysis through the access, for more than two-thirds of the dialysis sessions over a continuous 28-day period after access creation.*
4. Days of Central Venous Catheter (CVC) Exposure through 12 months
5. Subject Satisfaction using the Vascular Access Questionnaire (VAQ) at 6 months
6. Nurse-Cannulator Satisfaction at 3, 6, and 12 months
Subjective and objective parameters will be assessed including fistula characteristics, cannulator training, skills and experience cannulating this type of fistula.

5. Investigation Plan

This study is a prospective, non-randomized, multi-center, single-arm, observational, post-market surveillance (PS) study of the Ellipsys Vascular Access System. The study will be conducted by newly trained providers in subjects on hemodialysis and medically indicated for creation of an upper limb anastomosis. Subjects will be followed for 12 months (+2 month window) following the AVF creation procedure.

6. Determination of Sample Size

The sample size is not driven by a statistical hypothesis. To ensure that a minimum of 100 subjects will be evaluable at the 12-month follow-up visit, a minimum of 134 subjects will be enrolled in the study. This sample size estimate allows for a 25% drop-out rate ($100/.75 = 134$ subjects) which may result due to a higher than normal attrition rate seen in this study population due to the natural history of the disease state. Newly trained users from up to 14 sites in the United States will participate in the study. Each study site will enroll no more than 20% of the total enrollment (134 subjects), with a maximum of 27 subjects.

7. Statistical Methods

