7.1.3 Analysis Sets

The study populations are defined as follows:

- The **Safety population** is defined as all enrolled subjects in whom the procedure has been attempted and the Ellipsys Vascular Access System deployed, whether successful or not.

The Safety Population may include device failures. A device failure is defined as a malfunction of the Ellipsys Vascular Access System during use that precludes creation of a percutaneous AV fistula. A second Catheter may be deployed or a second Controller may be used to complete the procedure.

The Safety population may include procedure failures. A procedure failure is when the Ellipsys Vascular Access System is deployed and functions per specification, however, the AV fistula creation is unsuccessful due to incorrect placement in the patient anatomy. If this is observed immediately after deployment and the introducer sheath or guidewire is still in place, a second deployment may be attempted to complete the procedure.

- The **Treated population** is defined as all subjects in the Safety population with AVF successfully created.

Summaries of baseline parameters will be based on the Safety population. Summaries of the primary safety analyses will be based on the Safety population. Primary effectiveness and secondary endpoint analyses will be based on the Safety and/or Treated population, as indicated in the following sections. In the event a subject has more than one AVF access attempt, the first attempt will be used in summaries and analyses of the Safety population, and the final attempt will be used in summaries and analyses of the Treated population.

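### The percentage of subjects with a secondary procedure, and the 0/1/2/3/4+ split, make no allowance for early exit and so run low, unlike the person-years rate beside them

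*SAP*

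**What the plan says.** SAP 4.2.1, item 3 (and Protocol 4.1.4) states the endpoint as a percentage: "Defined as the percentage of subjects having one or more surgical or percutaneous interventions designed to mature or maintain the AVF or re-establish flow".

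The analysis method in SAP 7.7.4, repeated in Protocol 13.3.3, gives more than that:

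- A follow-up-adjusted rate: "Secondary procedure rate will be summarized cumulatively through 12 months as the number of procedures per person-years".
- In the same sentence, the percentage: "as well as the number and percentage of subjects having one or more procedures in the Treated population".
- A count table: "summarized categorically as the number and percentage of subjects with 0, 1, 2, 3, or 4 or more procedures".
- For PTA/balloon procedures, a further adjusted figure: "the rate of intervention in person-years, the location and average balloon size".

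The Treated population "is defined as all subjects in the Safety population with AVF successfully created"; completing follow-up is not a condition. Protocol 9.16 keeps subjects who stop early in the analysis and does not replace them. On attrition, SAP section 6 says: "To ensure that a minimum of 100 subjects will be evaluable at the 12-month follow-up visit, a minimum of 134 subjects will be enrolled", and "This sample size estimate allows for a 25% drop-out rate".

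Neither document gives a censoring or denominator rule for the percentage or the count table. SAP 7.3 has a rule for loss and death, but only for endpoints whose primary analysis is time-to-event.

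**The concern.** A percentage taken through 12 months means what it says only if subjects were observed for 12 months or could no longer have a procedure. Take a Treated subject who withdraws at month 3 without a procedure. That subject contributes a full unit to the denominator and nothing to the numerator, and sits in the 0 column of the count table. Missing follow-up can hide procedures but cannot create them, so the direction is fixed: the percentage is too low and the 0-procedure group too large. The mean procedure counts in the Additional Analysis of SAP 7.7.4 share the weakness.

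The plan deals with the same problem elsewhere. The patency, study-related SAE and functional cannulation endpoints use Kaplan-Meier with censoring. The interval AE percentages in SAP 7.8.3 count only subjects followed to the start of the interval.

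At stake is how the re-intervention burden reads in a surveillance study of newly trained providers. Part of the 0-procedure group would be subjects who left, not fistulas that needed nothing.

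**Working it through.** **The plan's own figure.** 100/0.75 = 133.3, rounded up to 134, so the stated enrolment reproduces. The 25% is attrition among enrolled subjects, from all causes.

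**Inputs.**
- From the documents: 25% total exit by 12 months (SAP section 6), applied here to Treated subjects as an assumption.
- Assumed: P, the 12-month percentage if nobody left, at 30, 50 and 70%; a constant procedure hazard; exits at a constant rate and independent of procedures.
- Assumed: q, the annual risk of death, at 0, 12.5% (half of 25%), 20% and 25%. Protocol 3.1 says one fifth of hemodialysis patients die each year, which motivates the 20%.

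**Formulas.** With h = −ln(1−P), c = −ln(0.75) = 0.2877 and d = −ln(1−q):

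- Crude percentage = h/(h+c) × [1 − (1−P)(0.75)].
- Cumulative incidence with death competing = h/(h+d) × [1 − (1−P)(1−q)].

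The cumulative incidence is the right comparator because a subject who dies without a procedure truly never had one.

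Example, P = 50%: crude = 0.6931/0.9808 × (1 − 0.375) = 44.2%. With q = 20%, cumulative incidence = 0.6931/0.9163 × (1 − 0.40) = 45.4%. The gap is 1.2 points.

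| P | Crude | Cumulative incidence (gap), no deaths | q = 12.5% | q = 20% | All exits deaths |
|---|---|---|---|---|---|
| 30% | 26.3% | 30.0% (3.7) | 28.2% (1.9) | 27.1% (0.8) | 26.3% (0) |
| 50% | 44.2% | 50.0% (5.8) | 47.2% (3.0) | 45.4% (1.2) | 44.2% (0) |
| 70% | 62.6% | 70.0% (7.4) | 66.4% (3.8) | 64.1% (1.6) | 62.6% (0) |

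For scale, if all 134 subjects were Treated, the standard error √(P(1−P)/134) is 4.0 to 4.3 points. The no-death gaps are about 0.9 to 1.9 standard errors, and the gaps at q = 20% about 0.2 to 0.4.

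**Early procedures.** Suppose all first procedures fall evenly in months 0 to 3, the 25% leave evenly over the year, and none die. Then crude = 0.75P + 0.25P(1 − 0.125) = 0.96875P. The gap is 1.6 points at P = 50% and 2.2 at 70%. A constant hazard with the same exit pattern gives 5.5 and 7.0.

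**Very common procedures.** The note in Protocol Table 6 reports PTA/balloon maturation in 99% of the pre-market study's subjects and expects similar procedures here. At P = 99%, with evenly spread exits and no deaths, crude is 93.9% (constant hazard) or 95.9% (months 0 to 3). The 0-procedure group is then 6.1% or 4.1% instead of 1%.

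**The count table.** At an assumed 2 procedures per year (Poisson, evenly spread exits, no deaths):

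| | 0 | 1 | 2 | 3 | 4+ | Mean count |
|---|---|---|---|---|---|---|
| Full follow-up | 13.5% | 27.1% | 27.1% | 18.0% | 14.3% | 2.0 |
| As tabulated | 21.0% | 27.7% | 24.3% | 15.3% | 11.7% | 1.75 |

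Mean follow-up is 0.75 + 0.25 × 0.5 = 0.875 years. The person-years rate is 1.75/0.875 = 2.0, which is correct when the rate is constant.

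**The case against.** A reader might infer that the secondary procedure rate is nothing but a crude percentage. The documents do not support that: the sentence opens with procedures per person-years, and a person-years figure is given again for PTA. That stands, and it limits the concern. It does not remove it. The person-years rate is not the endpoint SAP 4.2.1 defines, cannot give the share of subjects needing re-intervention, and sums up the year well only if the rate is roughly constant.

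A reader might also infer that 25% of subjects will be scored as procedure-free, or take 3.7 to 7.4 points as the expected bias. Neither follows. The 25% is planned attrition of enrolled subjects, which SAP section 6 ties to the natural history of the disease. It includes deaths, which add no bias, and subjects treated before leaving, who are counted correctly. Mortality here may be below one fifth, since eligibility requires a life expectancy of at least one year. The death share is simply unknown.

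Three further points are fair:

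- Scoring leavers as zero is inferred from silence; SAP 7.7.4 does not say so.
- The plan is not uniform elsewhere: SAP 7.8.3 also reports cumulative AEs as percentages of subjects.
- Primary patency (SAP 7.7.2) counts intervention as an event, with Kaplan-Meier, a death-competing curve and subcomponents. It excludes the specified maturation procedures, so it covers only part of this endpoint.

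**Conclusion.** The concern holds for the percentage and the count table, not for the secondary procedure summary as a whole. Followed as written, both treat Treated subjects who withdraw or are lost without a procedure as procedure-free to 12 months. The direction is certain wherever there is such loss; the size is not. Under 25% exit, a constant hazard and true rates of 30 to 70%, 3.7 to 7.4 points is the upper bound with no deaths. Deaths reduce it to about 1.9 to 3.8 points (half the exits), 0.8 to 1.6 points (20% annual death) or nothing (all exits). At any given death share it is smaller if procedures come early. The endpoint is descriptive, has no hypothesis test and is not among the planned pre-market comparisons, so sample size and error rates are unaffected. It is worth correcting because the affected figure is the endpoint as defined and the remedy is cheap.

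**What to change.** In SAP 7.7.4 and Protocol 13.3.3, keep the person-years rate and the raw counts, and add:

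1. The 12-month cumulative incidence of the first secondary procedure in the Treated population. Treat death and access abandonment as competing events and censor other exits at last follow-up. The cuminc call already in the SAP does this, with one more event code for abandonment.
2. Beside the 0/1/2/3/4+ table, the mean cumulative number of procedures per subject to 12 months and the number of subjects followed to 12 months.

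The cost is SAP and protocol wording and slightly more programming, mostly for the mean cumulative count. The reported percentage will be somewhat higher. The new estimate assumes that censored subjects would have needed procedures at the same rate as those who stayed; the text should say so.

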**Medtronic Business Restricted**

• Venous hypertension

• Secondary surgical intervention to repair vascular injuries

• Loss of site for percutaneous AV fistula creation

• Acute anastomotic or vessel disruption due to PTA or other catheter-based manipulation

			
--	--	--	--

There are no incremental risks introduced to the subject as a result of participation in this study.

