**Table 6: Adverse Event Causal Relationship Definitions**

Related to	Definition
Ellipsys System	Adverse events directly attributable to use of the device including introduction, use and removal from the vessel.
Study (Index) Procedure	
Adverse events that occur within 30 days of the index procedure where the Ellipsys System was used unless specifically shown not to be related to that index procedure.
 
Except the introduction, use and removal of the device including:
 
 
- initially accessing the vessel
 
- any catheter/wire exchanges during the study procedure not directly involving the study device, e.g., related to a completion angiogram
 

Secondary Procedure	Adverse events directly related to any aspect of the secondary procedure except the introduction, use and removal of device.
Intra-procedure (Index) PTA/balloon angioplasty or Planned PTA/balloon Maturation Procedure	
Adverse events directly related to the intra-procedure (index) or planned PTA/balloon maturation procedure (peri-procedure AEs and late AEs) including:
 
 
- introducing, inflating, deflating or removing the balloon catheter
 
- intimal injury, acute anastomotic disruption, extravasation, hematoma, pseudoaneurysm
 
- peri-anastomotic stenosis, intimal hyperplastic lesions
 

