**Medtronic Business Restricted**

**CONFIDENTIAL**

056-F275 Rev E Clinical Investigation Plan Template

	NOTE: As stated in the Ellipsys System IFU (available separate from the CIP), PTA/balloon maturation procedures to increase flow to the optimal access vessel was required in 99% of the Ellipsys IDE study subjects overall. The majority of these were performed to increase the anastomosis and juxta-anastomotic diameter and were unrelated to any clinical pathology. It is expected that similar procedures will be performed by the study investigator post-procedure and designated as such on the Secondary Procedure Form.
Cannulation	Adverse events directly related to cannulating a mature AV fistula target vessel to conduct dialysis, or other complications that can occur during or after dialysis such as bleeding, hematoma, etc.

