## Additional Analysis

- The association between the occurrence of acute anastomotic disruption or pseudoaneurysm and the secondary procedure rate for the Treated population. The mean number of secondary procedures will be summarized cumulatively and stratified by subjects who experienced anastomotic disruption or pseudoaneurysm and those who did not.
- The association between the occurrence of early occlusions and the secondary procedure rate for the Treated population. The mean number of secondary procedures will be summarized for subjects who experienced an early occlusion and those who did not.

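### The two association analyses of secondary procedures compare cumulative mean counts by ever/never event, with no time ordering or time at risk, so either contrast can mislead

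*SAP*

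**What the plan says.** Protocol 13.3.3 and SAP 7.7.4 carry the same two additional analyses in the Treated population. The first is announced as "The association between the occurrence of acute anastomotic disruption or pseudoaneurysm and the secondary procedure rate for the Treated population", and its statistic is "The mean number of secondary procedures will be summarized cumulatively and stratified by subjects who experienced anastomotic disruption or pseudoaneurysm", set against those without the event. The second concerns early occlusion: "The mean number of secondary procedures will be summarized for subjects who experienced an early occlusion and those who did not".

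The main summary in the same section has a time denominator: "Secondary procedure rate will be summarized cumulatively through 12 months as the number of procedures per person-years". It is specified overall and by procedure type, not for these two contrasts.

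The definition of what is counted is broad: "Secondary procedures are surgical or percutaneous interventions designed to mature or maintain the AVF or re-establish flow". Protocol 9.8 and 9.11 keep ballooning done during fistula creation out of that count.

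On cause, Protocol Table 6 lists "intimal injury, acute anastomotic disruption, extravasation, hematoma, pseudoaneurysm" among events directly related to index ballooning or a planned balloon maturation procedure. Protocol Table 4 lists "Acute anastomotic or vessel disruption due to PTA or other catheter-based manipulation". The note in Table 6 says that "PTA/balloon maturation procedures to increase flow to the optimal access vessel was required in 99% of the Ellipsys IDE study subjects overall", and that similar procedures are expected after the index and will be marked on the secondary procedure form.

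Abandonment is not among the exit reasons in Protocol 9.16.1 or SAP 7.1.1.

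**The concern.** Both analyses are introduced as associations with a rate, but what would be tabulated is procedures per subject, split by whether the event ever happened.

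For disruption or pseudoaneurysm, the procedures in the outcome can be the cause of the exposure. A subject with three maturation balloonings has had three chances of a balloon injury, and all three enter the mean. The event group is selected for high counts before any consequence of the event begins.

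For early occlusion, few procedures can come before an event that must occur by day 7, so ordering matters less. There the trouble is exposure. A fistula abandoned soon after occlusion collects few later procedures, yet its owner stays in the denominator. In the other direction, the procedure that reopens a salvaged fistula is counted as burden.

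At stake is how a surveillance report on newly trained providers describes the procedure burden that goes with these two complications. A reader will take a difference in means, or its absence, at face value.

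**Working it through.** **Plan figure.** The only design figure is enrollment: 100/0.75 = 133.3, rounded up to 134, which reproduces. The documents give no procedure rate, event risk or abandonment share, so every input below is an assumption.

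**A. Disruption or pseudoaneurysm caused by secondary procedures, with no effect on later procedures.** Let N be procedures per subject over 12 months, Poisson with mean λ. Each procedure causes the event with probability p.

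- Mean without event: λ(1−p).
- Mean with event: [λ − λ(1−p)e^(−λp)] / (1 − e^(−λp)).
- λ = 1.5, p = 0.05: without, 1.425. With, (1.5 − 1.425×0.9277)/0.0723 = 2.46. Ratio 1.73.

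| λ | p = 2% | p = 5% | p = 10% |
|---|---|---|---|
| 1 | 2.03 | 2.08 | 2.17 |
| 2 | 1.52 | 1.55 | 1.61 |
| 3 | 1.35 | 1.38 | 1.43 |

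A Poisson mean of 1.5 leaves 22% of subjects with no procedure, which sits poorly with the 99% figure in Table 6. So take N = 1 + Poisson(m−1), giving everyone at least one:

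- m = 1.5, p = 0.05: P(no event) = 0.95×e^(−0.025) = 0.9265. Mean without event = 1 + 0.5×0.95 = 1.475. With, (1.5 − 0.9265×1.475)/0.0735 = 1.82. Ratio 1.23.
- Over m = 1.2 to 2.0 and p = 3% to 10%, the ratio is 1.14 to 1.28.
- If half the event subjects had their event from index ballooning, they average 1.5 like anyone else. The event mean is (1.815 + 1.5)/2 = 1.66 and the ratio 1.12. Over the same grid it is 1.07 to 1.17.

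**B. Does a time denominator alone cure A?** Simulation of 400,000 subjects, Poisson model, p = 5%, 25% drop-out, true rate ratio 1.00:

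| λ | Raw mean ratio | Crude person-year ratio | Time-split ratio |
|---|---|---|---|
| 1 | 2.34 | 2.12 | 0.99 |
| 2 | 1.74 | 1.58 | 1.01 |
| 3 | 1.55 | 1.40 | 1.00 |

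The time-split ratio compares procedures after the event, per person-year after it, with procedures and person-time before it. The causing procedure stays in the before-event tally. Person-years alone do not remove the excess; ordering does.

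**C. Early occlusion at day 7.** A share a of these fistulas is abandoned at day 7. The rest have rate ratio R afterwards, and each salvaged fistula has k flow-restoring procedures. With t = 7/360, the mean is λt + (1−a)[k + Rλ(1−t)], against λ without occlusion.

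| λ | R | a | k | Mean, occluded vs not | Ratio |
|---|---|---|---|---|---|
| 1 | 1 | 25% | 0 | 0.75 vs 1.00 | 0.75 |
| 1 | 1 | 50% | 0 | 0.51 vs 1.00 | 0.51 |
| 1 | 1 | 25% | 1 | 1.50 vs 1.00 | 1.50 |
| 2 | 1 | 25% | 1 | 2.26 vs 2.00 | 1.13 |
| 1 | 2 | 50% | 0 | 1.00 vs 1.00 | 1.00 |

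Per fistula-year after day 7, with the treating procedure set apart, the ratio returns R in every row.

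**The case against.** The case for leaving the text alone has real substance.

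- **Silence is not content.** A reader might infer that the plan expressly counts the causing procedure. It does not say so. Inclusion follows from the word for cumulative counting and the lack of any exclusion. A programmer following the text would still count everything.
- **Not every event is affected.** A reader might infer that the excess arises by construction for all events. Table 6 covers index ballooning too, and events from it precede every counted procedure. The excess applies only to events caused by later procedures.
- **Not the only view of the question.** SAP 7.7.4 also tabulates procedures by indication, including an adverse event as the reason, and by link to adverse events. SAP 7.7.1 plans patency curves by early occlusion, and SAP 10.2 reports end-of-study fistula status, so abandonment after early occlusion will be visible. None of these compares later procedure rates.
- **Reversed sign for early occlusion.** With a doubled rate of 3.0 against 1.5 per year and 70% abandoned at day 14, the means are 3.0×(0.30 + 0.70×14/360) = 0.98 against 1.50. Nothing in the documents supports 70%, and adding the salvage procedure moves the result the other way. Only error in an unknown direction can be claimed.
- **The overall person-year rate.** A reader might infer that it is wrong too. SAP 7.7.4 does not say when its person-time ends. If 15% abandoned at month 3 and time ran on, total time would be inflated by 0.15×9/12 = 11% of full follow-up. That is conditional and not shown.

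The analyses are also descriptive and untested. That limits the consequences, but it does not make the contrast interpretable.

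**Conclusion.** The point holds for these two contrasts. As specified, the disruption or pseudoaneurysm comparison shows an excess without any effect of the event. The ratio is about 1.1 if every subject has a procedure and half the events come from the index, about 1.2 if all events come from later procedures, and up to about 2.2 under a plain Poisson model with full follow-up. Unequal drop-out can add a little. For early occlusion the raw mean can understate, hide or overstate the difference, and the documents do not show which.

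All sizes rest on assumed procedure rates, event risks and abandonment shares. The mechanism rests on the protocol's own account of what causes these events and on the absence of a time rule. The reach is narrow: additional descriptive analyses of one secondary endpoint. The primary endpoints and the sample size of 134 are untouched.

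**What to change.** Amend the additional analyses in SAP 7.7.4 and Protocol 13.3.3 together:

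- **Disruption or pseudoaneurysm.** Treat the event as time-varying. Report procedures per person-year with and without a prior event, counting in the with-event rate only procedures after the event date. Leave the causing procedure in the time before the event, and show causing and treating procedures separately.
- **Early occlusion.** Report procedures per fistula-year from a day-7 landmark, with a separate count for days 0-7. Starting the clock later without that count would drop the immediate rescue procedures. Place both beside the patency curves by early occlusion that are already planned.
- **Time at risk.** End person-time for these rates at abandonment, death or last follow-up.

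The cost is a few sentences and modest programming. The event, procedure and abandonment dates are already needed for the patency and adverse-event interval analyses. The downside is imprecision: at λ = 1.5 and p = 5%, about 7.2% of 134, or some 10 subjects, would have the event, so post-event rates should be given with confidence intervals and read cautiously.
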